## 9.2 Adverse Events

The definitions of an AE or serious adverse event (SAE) can be found in [Appendix 3](#).

AEs will be reported by the participant (or, when appropriate, by a caregiver, surrogate, or the participant's legally authorized representative).

The Investigator and any designees are responsible for detecting, documenting, and reporting events that meet the definition of an AE or SAE and remain responsible for following up AEs that

are serious, considered related to the study treatment or the study, or that caused the participant to discontinue before completing the study.

Immune-mediated AEs are AEs consistent with an immune-mediated mechanism or immune-mediated component for which non-inflammatory etiologies (eg, infection or tumor progression) have been ruled out. IMAEs can include events with an alternate etiology which were exacerbated by the induction of autoimmunity. Information supporting the assessment will be collected on the participant's CRF.

**Contacts for SAE reporting are specified in [Appendix 3](#).**

### **9.2.1 Time Period and Frequency for Collecting AE and SAE Information**

The collection of non-serious AE information (with the exception of non-serious AEs related to [REDACTED]) should begin at initiation of study treatment until the time points specified in the Schedule of Activities ([Section 2](#)). Non-serious AE information should also be collected from the start of a placebo lead-in period or other observational period intended to establish a baseline status for the participants.

Section 5.6.1 and 5.6.2 in the IBs for relatlimab, nivolumab, BMS-986205, and ipilimumab, represent the Reference Safety Information, to determine expectedness of SAEs for expedited reporting. Following the participant's written consent to participate in the study, all SAEs, whether related or not related to study drug, must be collected, including those thought to be associated with protocol-specified procedures.

All SAEs must be collected that occur during the screening period and within [REDACTED] of the last dose of study treatment. For participants assigned to treatment and never treated with study drug, SAEs should be collected for [REDACTED] from the date of treatment assignment. If applicable, SAEs must be collected that relate to any later protocol-specified procedure (eg, a follow-up skin biopsy). All SAEs, and all AEs (SAEs and non-serious AEs) associated with confirmed or suspected [REDACTED] infection must be collected from the date of the participant's written consent until [REDACTED] following discontinuation of dosing.

The Investigator must report any SAE that occurs after these time periods and that is believed to be related to study drug or protocol-specified procedure:

- Medical occurrences that begin before the start of study treatment but after obtaining informed consent will be recorded on the appropriate section of the eCRF section.
- All SAEs will be recorded and reported to the Sponsor or designee within 24 hours, as indicated in [Appendix 3](#).
- The Investigator will submit any updated SAE data to the Sponsor within 24 hours of updated information being available.

Investigators are not obligated to actively seek AEs or SAEs in former study participants; however, if the Investigator learns of any SAE, including a death, at any time after a participant has been

discharged from the study, and he/she considers the event reasonably related to the study treatment or study participation, the Investigator must promptly notify the Sponsor.

The method of evaluating and assessing causality of AEs and SAEs and the procedures for completing and reporting/transmitting SAE reports are provided in [Appendix 3](#).

### **9.2.2 Method of Detecting AEs and SAEs**

AEs can be spontaneously reported or elicited during open-ended questioning, examination, or evaluation of a participant. Care should be taken not to introduce bias when collecting AEs and/or SAEs. Inquiry about specific AEs should be guided by clinical judgement in the context of known AEs, when appropriate for the program or protocol.

Every adverse event must be assessed by the investigator with regard to whether it is considered immune-mediated. For events which are potentially immune-mediated, additional information will be collected on the participant's case report form.

### **9.2.3 Follow-up of AEs and SAEs**

- Non-serious AEs should be followed to resolution or stabilization, or reported as SAEs if they become serious (see [Appendix 3](#)).
- Follow-up is also required for non-serious AEs that cause interruption or discontinuation of study treatment and for those present at the end of study treatment, as appropriate.
- All identified non-serious AEs must be recorded and described on the non-serious AE page of the CRF (paper or electronic). Completion of supplemental CRFs may be requested for AEs and/or laboratory abnormalities that are reported/identified during the course of the study.

After the initial AE/SAE report, the Investigator is required to proactively follow each participant at subsequent visits/contacts. All SAEs, and non-serious AEs of special interest (as defined in [Section 9.2](#)) and AEs (SAEs and non-serious AEs) associated with confirmed or suspected [REDACTED] will be followed until resolution, until the condition stabilizes, until the event is otherwise explained, the event is deemed irreversible, or until the participant is lost to follow-up (as defined in [Section 8.3](#)).

Further information on follow-up procedures is given in [Appendix 3](#).

### **9.2.4 Regulatory Reporting Requirements for SAEs**

- Prompt notification of SAEs by the Investigator to the Sponsor is essential so that legal obligations and ethical responsibilities towards the safety of participants and the safety of a product under clinical investigation are met.
- An Investigator who receives an Investigator safety report describing SAEs or other specific safety information (eg, summary or listing of SAEs) from the Sponsor will file it along with the IB and will notify the IRB/IEC, if appropriate according to local requirements.

The Sponsor or designee will be reporting AEs to regulatory authorities and Ethics Committees according to local applicable laws, including European Directive 2001/20/EC and FDA Code of

Federal Regulations 21 CFR Parts 312 and 320. Suspected, unexpected serious adverse reactions (SUSARs) are a subset of SAEs and will be reported to the appropriate regulatory authorities and Investigators following local and global guidelines and requirements.

#### **9.2.6      *Pregnancy***

If, following initiation of the study treatment, it is subsequently discovered that a participant is pregnant or may have been pregnant at the time of study exposure, including during at least 5 half-lives after product administration, the Investigator must immediately notify the BMS Medical Monitor/designee of this event and complete and forward a Pregnancy Surveillance Form to BMS or designee within 24 hours of awareness of the event and in accordance with SAE reporting procedures described in Appendix 3.

If the Investigator determines a possible favorable benefit-risk ratio that warrants continuation of study treatment, or reinitiation of study treatment, a discussion between the Investigator and the BMS Medical Monitor/designee must occur. If, for whatever reason, the pregnancy has ended, confirmed by negative serum pregnancy test, treatment may be resumed (at least 3 weeks and not greater than 6 weeks after the pregnancy has ended), following approvals of participant/Sponsor/IRB/EC, as applicable.

Follow-up information regarding the course of the pregnancy, including perinatal and neonatal outcome and, where applicable, offspring information must be reported on the Pregnancy Surveillance Form.

Any pregnancy that occurs in a female partner of a male study participant should be reported to the Sponsor or designee. In order for the Sponsor or designee to collect any pregnancy surveillance information from the female partner, the female partner must sign an ICF for disclosure of this information. Information on this pregnancy will be collected on the Pregnancy Surveillance Form.

### **9.2.7 Laboratory Test Result Abnormalities**

The following laboratory test result abnormalities should be captured on the non-serious AE CRF page or electronic SAE Report Form, as appropriate. Paper forms are only intended as a back-up option when the electronic system is not functioning.

- Any laboratory test result that is clinically significant or meets the definition of an SAE.
- Any laboratory test result abnormality that required the participant to have study treatment discontinued or interrupted.
- Any laboratory test result abnormality that required the participant to receive specific corrective therapy.

It is expected, that wherever possible, the clinical rather than laboratory term will be used by the reporting Investigator (eg, anemia vs low hemoglobin value).

### **9.2.8 Potential Drug Induced Liver Injury**

Wherever possible, timely confirmation of initial liver-related laboratory abnormalities should occur prior to the reporting of a potential DILI event. All occurrences of potential DILIs, meeting the defined criteria, must be reported as SAEs. See [Section 9.2](#) and [Appendix 3](#) for reporting details.

Potential DILI is defined as:

- 1) Aminotransaminase (AT; ALT or AST) elevation  $>3 \times \text{ULN}$ .

AND

- 2) Total bilirubin  $>2 \times \text{ULN}$ , without initial findings of cholestasis (elevated serum alkaline phosphatase).

AND

- 3) No other immediately apparent possible causes of AT elevation and hyperbilirubinemia, including, but not limited to, viral hepatitis, pre-existing chronic or acute liver disease, or the administration of other drug(s) known to be hepatotoxic.

### **9.2.9 Other Safety Considerations**

Any significant worsening noted during interim or final physical examinations, ECG, x-ray filming, or any other potential safety assessment required or not required by protocol, should also be recorded as a non-serious AE or SAE, as appropriate, and reported accordingly.

### 9.3 Overdose

An overdose is defined as the accidental or intentional administration of any dose of a product that is considered both excessive and medically important. Overdose, as a verbatim term (as reported by the investigator), should not be reported as an AE/SAE unless it is an intentional overdose taken with possible suicidal/self-harming intent. Such overdoses should be reported regardless of sequelae and should specify “intentional overdose” as the verbatim term (see [Section 9.2](#)).

For this study, any dose of relatlimab, nivolumab, BMS-986205, or ipilimumab greater than the planned dose will be considered an overdose.

In the event of an overdose the Investigator/treating physician should:

- 1) Contact the Medical Monitor immediately.
- 2) Closely monitor the participant for AEs/SAEs and laboratory abnormalities until study treatment can no longer be detected systemically (at least [REDACTED]).
- 3) Document the quantity of the excess dose as well as the duration of the overdose in the CRF.

Decisions regarding dose interruptions or modifications will be made by the Investigator in consultation with the Medical Monitor based on the clinical evaluation of the participant.

### 9.4 Safety

Planned time points for all safety assessments are listed in the Schedule of Activities (see [Section 2](#)).

#### 9.4.1 Physical Examinations

Refer to [Schedule of Activities](#).

#### 9.4.2 Vital signs

Refer to Schedule of Activities.

#### 9.4.3 Electrocardiograms

Refer to Schedule of Activities.

#### 9.4.4 Clinical Safety Laboratory Assessments

- Investigators must document their review of each laboratory safety report.
- Local laboratory tests may be used to guide clinical decisions and determine eligibility for dose administration once eligibility to participate in this study has been confirmed by central laboratory results.

A central/local laboratory will perform the analyses and provide reference ranges for these tests.

During screening and treatment, unless otherwise indicated in [Table 9.4.4-1](#), results of clinical laboratory tests must be reviewed prior to dose administration.

**Table 9.4.4-1: Laboratory Assessments**

Hematology	
Hemoglobin	
Hematocrit	
Total leukocyte count, including differential	
Platelet count	
Methemoglobin; if elevated, draw reticulocyte count, lactate dehydrogenase (LDH), and haptoglobin. Methemoglobin is assessed on arterial or venous blood sample	
G6PD levels; prior to treatment assignment only, if indicated	
Serum Chemistry	
Aspartate aminotransferase (AST)	Total Protein
Alanine aminotransferase (ALT)	Albumin
Total bilirubin	Sodium
Direct bilirubin; reflex if total is abnormal	Potassium
Alkaline phosphatase	Chloride
Lactate dehydrogenase	Calcium
Creatinine	Phosphorus
(b) (see below)	Magnesium
Blood urea nitrogen (BUN)	Creatinine clearance; screening only; Cockcroft-Gault formula
Uric acid	Cardiac troponin T (cTnT) or I (cTnI); see below
Glucose	Amylase
C-reactive protein	Thyroid-stimulating hormone (TSH), free T3 and free T4 - screening; see below
Lipase	
Gamma glutamyl transferase; reflex when alkaline phosphatase is Grade $\geq$ 2	
HbA1c; obtain during screening to establish baseline in participants with type 2 diabetes, then as clinically indicated	
Endocrine Panel	
TSH with reflex to free T3 and free T4 as applicable on-treatment	
Participants with controlled hyperthyroidism must be negative for thyroglobulin and thyroid peroxidase antibodies and thyroid stimulating immunoglobulin; screening only.	

**Table 9.4.4-1: Laboratory Assessments**

Urinalysis
Protein
Glucose
Blood
Leukocyte esterase
pH
Microscopic examination of the sediment if blood, protein or leukocytes esterase are positive on the dipstick
Serology (at screening only)
Hepatitis A antibody
Hepatitis C antibody; if hepatitis C antibody is positive, reflex to hepatitis C RNA
Hepatitis B surface antigen (HBsAg) and/or hepatitis B core antigen
HIV-1, and -2 antibody where mandated by local requirements
Other Analyses
Pregnancy test (WOCBP only: minimum sensitivity 25 IU/L or equivalent units of human chorionic gonadotropin [hCG])
Follicle stimulating hormone (FSH) screening - only required to confirm menopause in women < age 55) as defined in Appendix 4
Serologic tumor marker for gastric cancer, carcinoembryonic antigen (CEA)

Abbreviations: ALT = alanine aminotransferase; AST = aspartate aminotransferase; BUN = blood urea nitrogen; CEA = carcinoembryonic antigen; [REDACTED]; T; FSH = follicle stimulating hormone; GP6D = glucose-6-phosphate dehydrogenase; HbA1c = glycated hemoglobin; HBSAg = hepatitis B surface antigen; HCG = human chorionic gonadotropin; HIV-1 = human immunodeficiency virus-1; HIV-2 = human immunodeficiency virus-2; LDH = lactate dehydrogenase; RNA = ribonucleic acid; TSH = thyroid-stimulating hormone WOCBP = women of child bearing potential.

#### **9.4.5 Imaging Safety Assessment**

Any incidental findings of potential clinical relevance that are not directly associated with the objectives of the protocol should be evaluated and handled by the study Investigator per standard medical/clinical judgment.

[REDACTED]

[figure not shown]

[figure not shown]

### **9.8.3      *Additional Research Collection***

This protocol will include residual sample storage for additional research.

#### **For All US Sites:**

Additional research participation is required for all investigational sites in the U.S.

#### **For Non-US Sites:**

Additional research is optional for all study participants, except where retention and/or collection is prohibited by local laws or regulations, ethics committees, or institutional requirements.

This retention for additional research is intended to expand the translational Research and Development capability at BMS, and will support as yet undefined research aims that will advance our understanding of disease and options for treatment. It may also be used to support health authority requests for analysis, and advancement of pharmacodiagnostic development to better

target drugs to the right patients. This may also include genetic/genomic exploration aimed at exploring disease pathways, progression and response to treatment, etc.

### **Sample Collection and Storage**

All requests for access to samples or data for additional research will be vetted through a diverse committee of the study Sponsor's senior leaders in Research and Development (or designee) to ensure the research supports appropriate and well-defined scientific research activities.

- [REDACTED]

Samples kept for future research will be stored at the BMS Biorepository in [REDACTED] or an independent, BMS-approved storage vendor.

The manager of these samples will ensure they are properly used throughout their usable life and will destroy the samples at the end of the scheduled storage period, no longer than fifteen (15) years after the end of the study or the maximum allowed by applicable law.

Transfers of samples by the research Sponsor to third parties will be subject to the recipient's agreement to establish similar storage procedures.

Samples will be stored in a coded fashion, and no researcher will have access to the key. The key is securely held by the Investigator at the clinical site, so there is no direct ability for a researcher to connect a sample to a specific individual.

Further details of sample collection and processing will be provided to the site in the Procedure Manual.

## **10 STATISTICAL CONSIDERATIONS**

### **10.1 Sample Size Determination**

## 10.2 Populations for Analyses

For purposes of analysis, the following populations are defined:

Population	Description
Enrolled	All participants who sign informed consent and are registered into the IRT
Treated	All participants who take at least 1 dose of study treatment
Response-evaluable	All treated participants with measurable disease at baseline and 1 of the following: a) at least 1 post-baseline tumor assessment; b) clinical progression, or c) death
[REDACTED]	[REDACTED]
[REDACTED]	[REDACTED]
[REDACTED]	[REDACTED]

Abbreviations: IRT = interactive response technology; [REDACTED].

## 10.3 Statistical Analyses

Final analysis will be performed after all participants are enrolled and have been followed for the minimum time to evaluate the primary endpoint. The statistical analysis plan will be developed and finalized before the database lock for the final analysis. A description of the participant population will be included in the statistical output reported, including subgroup of age, gender, and race. Below is a summary of planned statistical analyses of the primary and secondary endpoints. In general, summaries will be performed by dose level, cohort, and indication. If sufficient data are not available such that adequate interpretation of the result is not warranted, some summaries may not be performed and only listings will be presented.

[REDACTED]

### 10.3.1 Efficacy Analyses

The primary efficacy analyses will be performed on the treated population for the final analysis. Efficacy analyses based on the response-evaluable population may be performed for interim analyses when the minimum follow-up period is less than sufficient to warrant adequate interpretation of the result. Efficacy analyses may be performed on selected subgroups, including biomarker-selected subgroups. Efficacy analyses will be performed using the RECIST v1.1 criteria. Additional details on efficacy analyses are provided in [Table 10.3.1-1](#).

**Table 10.3.1-1: Overview of Efficacy Analysis Methods**

Endpoint	Statistical Analysis Methods

ORR is defined as the proportion of participants whose BOR is either CR or PR. DCR is defined as the proportion of participants whose BOR includes CR, PR, and SD.
 
Best overall response per RECIST v1.1 is defined as the best response designation recorded between the date of first dose and the date of first objectively documented progression per RECIST v1.1 or the date of subsequent therapy, whichever occurs first. For participants who continue treatment beyond progression per RECIST v1.1 or begin subsequent therapy, the BOR should be determined based on response designations recorded up to the time of the initial progression or subsequent therapy, whichever occurs first. For participants without documented progression or subsequent therapy, all available response designations should contribute to the BOR assessment.
	
Estimate of ORR and DCR and corresponding 2-sided exact 95% CI using the Clopper-Pearson method.

mDOR
 
DOR for a participant with a BOR of CR or PR is defined as the time between the date of first response and the date of the first objectively documented tumor progression per RECIST v1.1 or death, whichever occurs first. For those participants who neither progress nor die, the duration of objective response will be censored at the same time they will be censored for the primary definition of PFS.
	
Estimate by the Kaplan-Meier method and corresponding 2-sided 95% CI using Brookmeyer and Crowley methodology (using log-log transformation).


mPFS and PFSR at 6 and 12 months
 
PFS is defined as the time from first dose to the date of first objectively documented progression, per RECIST v1.1, or death due to any cause, whichever occurs first. Clinical deterioration in the absence of objectively documented progression per RECIST v1.1 is not considered progression for the purpose of determining PFS. Participants who die without a reported progression will be considered to have progressed on the date of their death. Participants who did not progress or die will be censored on the date of their last evaluable tumor assessment. Participants who did not have any on study tumor assessments and did not die will be censored on the date of first dose. Participants who started any subsequent anticancer therapy, including tumor-directed radiotherapy and tumor-directed surgery, without a prior reported progression will be censored at the last evaluable tumor assessment prior to initiation of the subsequent anticancer therapy. The PFSR at time T is defined as the probability that a participant has not progressed and is alive at time T following first dose.
	
Estimate by the Kaplan-Meier method and corresponding 2-sided 95% CI using Brookmeyer and Crowley methodology (using log-log transformation) for the median and Greenwood formula for the rate.

Abbreviations: BOR = best overall response; CI = confidence interval; CR = complete response; DCR = disease control rate; DOR = duration of response; mDOR = median duration of response; mPFS = median progression-free survival; [REDACTED] ORR = overall response rate; [REDACTED] PFS = progression-free survival; PFSR = progression-free survival rate; PR = partial response; RECIST = Response Evaluation Criteria in Solid Tumors; SD = stable disease; T= time.

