### **7.7.4 Palliative Local Therapy**

Palliative and supportive care for disease-related symptoms may be offered to all participants on the trial; however, Investigators should consult with the BMS Medical Monitor prior to initiating palliative radiation in participants who have not yet completed the DLT evaluation period. Limited radiation therapy or surgery to control isolated lesions is permitted for participants who have Investigator-assessed clinical benefit following consultation with the BMS Medical Monitor. Participants should not receive study drug treatment during radiation, as the potential for overlapping toxicities with radiotherapy and the triplet combinations is currently not known. Anecdotal data suggest that radiotherapy administered to participants while receiving nivolumab therapy is tolerable; however, because concurrent radiotherapy and immunotherapies in cancer have not been formally evaluated, in cases where palliative radiotherapy is required for a tumor lesion, study treatment should be withheld for at least 1 week before, during, and 1 week after radiation. Participants should be closely monitored for any potential toxicity during and after receiving radiotherapy, and AEs related to radiotherapy should resolve to Grade 1 prior to resuming study drug.

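### DOR is censored at subsequent therapy only for responders who never progress or die, so the censoring time depends on the later outcome and DOR departs from the BOR and PFS rules

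*Combined protocol and SAP*

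**What the plan says.** All the rules sit in Table 10.3.1-1 (Section 10.3.1).

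- **DOR, event.** From first response to "the date of the first objectively documented tumor progression per RECIST v1.1 or death, whichever occurs first". Subsequent therapy is not mentioned.
- **DOR, censoring.** "For those participants who neither progress nor die, the duration of objective response will be censored at the same time they will be censored" under the primary definition of PFS. The PFS censoring times are borrowed only for responders with neither event.
- **PFS, subsequent therapy.** Those who start other anticancer treatment (local radiation or an operation on the tumor counts) "without a prior reported progression will be censored at the last evaluable tumor assessment prior to initiation of the subsequent anticancer therapy". This carries no condition on what happens later.
- **PFS, death.** "Participants who die without a reported progression will be considered to have progressed on the date of their death".
- **BOR.** For participants treated past progression or starting other therapy, "the BOR should be determined based on response designations recorded up to the time of the initial progression or subsequent therapy, whichever occurs first".

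Table 4-1 lists median DOR as a primary endpoint with ORR and DCR. It is estimated by Kaplan-Meier. Section 7.7.4 shows one route to local therapy without progression: "Limited radiation therapy or surgery to control isolated lesions is permitted for participants who have Investigator-assessed clinical benefit", after consultation with the Medical Monitor.

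**The concern.** Kaplan-Meier needs a censoring time that does not depend on what happens to the participant afterwards. The DOR rule, followed literally, breaks this. Whether a responder who switches therapy keeps the follow-up after the switch is decided by whether an event occurs in it: if so, the time and the event are both kept; if not, the time is deleted back to the scan before the switch.

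Two coherent quantities are available: duration with everyone censored at new therapy, and duration regardless of new therapy. The written rule estimates neither. It also separates DOR from its companion endpoints. A responder who switches and then progresses is censored for PFS before the switch but is a DOR event after it. At stake is the interpretation of a primary endpoint, and the chance that two programmers would censor the same participants differently.

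**Working it through.** **No figure to reproduce.** The visible text gives no DOR estimate, number of responders, switching rate or power statement for median DOR.

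**The rules side by side.** Two responders start new therapy after a scan at month 4, without progression. One dies at month 12; the other is event-free at month 20.

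| Rule | Dies at 12 | Event-free at 20 |
|---|---|---|
| DOR as written | event at 12 | censored at 4 |
| PFS subsequent-therapy rule | censored at 4 | censored at 4 |
| Regardless of new therapy | event at 12 | censored at 20 |

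**Ten-responder illustration (hypothetical).** Add eight responders who do not switch: one event before month 4, three between months 4 and 12, one at month 14, three later.

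- As written: 9/10 = 0.900; one is censored at 4, leaving 8 at risk; after three events 0.900 × 5/8 = 0.563; the death at 12 gives 0.900 × 4/8 = 0.450. Median 12 months.
- PFS rule: both are censored at 4, leaving 7 at risk; after three events 0.900 × 4/7 = 0.514; the event at 14 gives 0.900 × 3/7 = 0.386. Median 14 months.
- Regardless of new therapy: five events in ten by month 12 gives 0.500. Median 12 months, on a higher curve than as written.

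**Size in a larger model.** Every input is an assumption. DOR is exponential with median 12 months, so h = ln 2/12 = 0.0578 per month. The time to switch is independent and exponential with hazard h·p/(1−p), where p is the share who would switch before an event. The hazard is unchanged after a switch. Follow-up is uniform over 12-30 months. Values of p of 0.10, 0.20, 0.30 and 0.35 give about 7%, 15%, 24% and 29% observed switchers. True 18-month DOR is 2^(−18/12) = 35.4%. There were 600,000 simulated responders per scenario.

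With all progression after the switch captured:

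| Observed switchers | Median as written | 18-month DOR as written | Either coherent rule |
|---|---|---|---|
| 7% | 11.8 | 34.1% | 12.0; 35.3% |
| 15% | 11.5 | 32.5% | 12.0; 35.3% |
| 24% | 11.2 | 30.6% | 12.0; 35.3% |
| 29% | 11.1 | 29.5% | 12.0; 35.3% |

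The shift in the median is 0.2 to 0.9 months. Shorter follow-up enlarges it: at 6-24 months with 29% observed switchers the median is 10.6, which is 1.4 months low.

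With only deaths captured after the switch (12-30 months' follow-up, mean lag from unseen progression to death of 6, 10 or 15 months, 6-30% switchers), the as-written median is 11.9-12.1 months against 12.0 under the PFS rule. The 18-month DOR is 32.2-35.1% against 35.3%.

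**Wider assumptions.** With a post-switch hazard ratio of 0.5, 1 or 2, follow-up of 6-24 or 12-36 months and 6-35% observed switchers, the as-written median runs from 9.8 to 12.0 months with progression captured, and from 11.3 to 12.3 with deaths only. The PFS rule gives 11.9-12.1 throughout, because switching is unrelated to prognosis in the model.

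**The case against.** **The wording may be shorthand.** Tying DOR to PFS censoring suggests that the condition was meant as the absence of a PFS event. Section 10.3 calls the text a summary and defers detail to an analysis plan due before database lock. That is a fair reading of intent, but nothing supplied says it, and literal programming gives the incoherent rule.

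**A reader might infer a fixed downward bias.** The documents do not support that. Section 5.1.2 lists the start of subsequent treatment among the points at which tumor assessments end, so after a systemic switch mainly deaths may be seen. The median is then nearly unaffected, with no fixed sign. Even capture of deaths is uncertain: Section 5.1.6 starts survival follow-up for Part B participants, while Table 2-4 heads it for all participants.

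**A reader might infer from Section 7.7.4 that responders are the ones affected.** The section concerns limited therapy to isolated lesions and clinical benefit, which is not confined to CR or PR, and it gives no frequency. It shows only that the situation can arise.

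**The error is small against sampling noise.** With an assumed 10-50 responders, the standard deviation of the estimated median in the same model is about 4.8 to 2.6 months, and no visible decision rule uses median DOR. This lowers the severity but does not make the rule coherent.

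**Censoring at new therapy may itself be informative** if responders switch because they are worsening. This stands, and is why the fix includes a sensitivity analysis.

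**Conclusion.** The DOR rule is wrong as written: its censoring time depends on the later outcome, and it does not match the BOR and PFS rules in the same table. The size and direction of the bias are unknown, because the documents give no switching rate and leave open what is captured after a switch. Under the assumptions above (median 12 months, unchanged hazard, 12-30 months' follow-up, 7-29% switchers), the median is about 0.2-0.9 months low if later progression is captured. It is roughly unbiased, with 18-month DOR slightly low, if only deaths are captured.

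The overlap in the PFS cell is a lesser matter. Someone who switches without progression and then dies meets both the death sentence and the subsequent-therapy sentence. The specific rule reads naturally as an exception to the general one, so stating precedence is a clarification.

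Severity: should be fixed. A stronger grade would need evidence of a material bias or of a decision resting on median DOR, and the visible text has neither.

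**What to change.** Replace the DOR censoring sentence with a rule to this effect: responders who start subsequent anticancer therapy (including tumor-directed radiotherapy or surgery) without prior documented progression are censored for DOR at the last evaluable tumor assessment before that therapy, regardless of later progression or death; other responders without progression or death are censored at their last evaluable assessment.

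In the PFS cell, state that the subsequent-therapy rule takes precedence over the death rule. Report DOR counting events regardless of subsequent therapy as a sensitivity analysis, with the number of responders who switched before progression and what was captured afterwards.

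The cost is two sentences in Table 10.3.1-1 or the analysis plan, plus one sensitivity analysis, settled before database lock. No new data are needed. The downside is that a few events become censored, with a small loss of precision.
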